Cohort B: Healthy volunteers, steady state TFV-based regimen (either on daily TFV- based PrEP or taking daily TFV-based regimen 7 days prior to procedure) (PrEP Cohort)

Cohort C: Persons infected with HIV taking TFV/FTC-based HIV treatment (ARV Cohort)

Inclusion Criteria

Participants who meet the following criteria are eligible for inclusion in this research:

1. English speaking male or female volunteers between the ages of 18-50 for younger adults or 65-80 for older adults
2. Willing to provide written informed consent
3. Willing to abstain from insertion of anything in rectum for 72 hours before and 72 hours after the endoscopic procedure for colorectal tissue collection.
4. Not currently participating in other research studies involving drugs and/or medical devices.

For participants not infected with HIV (Control Cohort A)

1. No known risk for HIV exposure or a documented negative HIV-1/HIV-2 Ag/Ab test in the past 3 months (HIV risk, but not on PrEP)
2. Documented negative HBsAg in those taking study TFV (i.e. cohort B)

For participants not infected with HIV, but taking or willing to take TFV (PrEP Cohort B)

1. Currently taking TFV-based oral PrEP daily or willing to take oral TFV-containing PrEP for one week
2. Documented negative HIV-1/HIV-2 Ag/Ab test in the past 3 months
3. Documented negative HBsAg

For participants infected with HIV (ARV Cohort C)

1. Virologically suppressed HIV for at least 6 months prior to screening.
2. Taking tenofovir disoproxil fumarate or tenofovir alafenamide containing regimen to treat HIV

Exclusion Criteria

Participants who meet any of the following criteria at screening will be excluded from the study:

1. History of inflammatory bowel disease or active inflammatory condition of the GI tract
2. History of significant gastrointestinal bleeding
3. Current medically-indicated use of warfarin or heparin or other anticoagulant medications associated with increased risk for bleeding following mucosal biopsy (e.g., daily high dose aspirin [>81 mg], non-steroidal anti-inflammatory drugs [NSAIDs], or Pradaxa®)
4. Use of systemic immunomodulatory medications within 4 weeks of enrollment
5. Use of rectally administered medications within 4 weeks of enrollment
6. Use of product containing nonoxynol-9 within 4 weeks of enrollment
7. Use of any investigational products within 4 weeks of enrollment

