Clinical	
 • Obtain complete medical history, documenting pre-existing conditions • Review and record concomitant medications • Obtain vital signs – blood pressure (BP), heart rate (HR), height, and weight (height may be obtained from EMR, and weight captured in the EMR within 6 months of screening may be obtained from EMR 
Note: Medical history and physical examination data may be extracted from electronic medical record, or performed at the time the participant presents for an endoscopic procedure scheduled for clinical indication.

Safety Labs and STI Screening (for participants not undergoing a concurrent endoscopy procedure only):	
 • Perform general physical exam • Collect rectal swab for GC/CT • Collect blood specimens for: 
 ○ Complete blood count (CBC) with differential¹ ○ AST, ALT, BUN, Creatinine¹ ○ HIV testing² ○ Syphilis testing³
PrEP cohort only for those not already on TFV-based PrEP prior to screening	
 • HBsAg (result from prior test within 12 months acceptable) • Dispense F/TDF or F/TAF for daily dosing to begin 7 days prior to study procedure (PrEP Cohort B only, not already on PrEP) • Commence daily virtual DOT for 7 days prior to study procedure

¹ Screening laboratory values are valid up to 42 days.

²See Appendix II: HIV Testing Algorithm; HIV testing not to be done in participants known to be infected with HIV

³Syphilis Chemiluminescence assay (with confirmatory RPR; FTA-ABS performed on RPR negative samples)

Visit 2: Sampling Visit (\leq 42 days since Screening Visit)

Note: Where applicable, Visit 2 may be combined with Visit 1

After eligibility is confirmed, participants will be contacted to schedule the study visit (Visit 2). Where possible, Study Visit 2 may be coordinated with a scheduled clinical procedure, such as a screening colonoscopy.

The following activities will take place at the Study Visit:

Table 2: Visit 2 – Sampling Visit

Component	Procedure/Analysis
Administrative	
 Confirm participant understood and signed informed consent Review/update locator information Confirm eligibility Provide counseling: 
 HIV/STI risk reduction counseling Provide a copy of pre- and post- visit reminders

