Participants will be screened and excluded if taking any blood thinners or have conditions that may prolong bleeding. Risk of perforation, which is a medical emergency that may require surgery, will be minimized by enrolling participants who do not have significant bowel disease and having the procedure performed by a credentialed endoscopist. Where possible, the endoscopic procedure will be paired with a procedure that may have a clinical indication, such as screening colonoscopy for colon cancer. In this case, the only additional risk to the participant are the risks of collecting pinch biopsies, which are lower in risk than the endoscopy itself..

Phlebotomy is performed by drawing blood from a vein in the forearm or antecubital fossa. This may cause pain during the insertion of the needle or slight bruising afterward.

TFV (administered as part of this research protocol): TFV disoproxil fumarate (TDF) and TFV alafenamide (TAF) are both TFV prodrugs licensed by FDA for the prevention and treatment of HIV. TFV-based PrEP regimens currently approved include emtricitabine / tenofovir alafenamide (F/TAF) or emtricitabine / tenofovir disoproxil fumarate (F/TDF). Both combination regimens are well tolerated. Risks of TFV include acute exacerbation of hepatitis B virus Immune Reconstitution Syndrome; New or worsening renal impairment; lactic acidosis; hepatomegaly with steatosis; lower bone mineral density; diarrhea; nausea; headache; fatigue; abdominal pain; rash. Risks will be minimized by confirming participants do not have hepatitis B or HIV and baseline safety labs will be monitored prior to receiving study medication. TFV-naïve participants who are not already prescribed TFV-containing regimens for PrEP or treatment will take only 7 doses, which will minimize the risks associated with chronic administration.

STI testing: Participants may become embarrassed, worried, or anxious when completing their HIV-related interviews and/or receiving STI counseling. Certain positive results (Chlamydia, gonorrhea) may need to be reported to appropriate Department of Public Health Agencies. The reporting only happens if the test result is positive and is always done confidentially.

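### For Cohort B starters, study tenofovir is dispensed at the screening visit with no stated hold for HBsAg and HIV results, which does not fit the safeguard promised before drug is received

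*Combined protocol and SAP*

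**What the plan says.** Section VIII (Risks, paragraph on study-administered TFV) lists hepatitis B exacerbation and renal impairment among the risks. It says they are minimized by "confirming participants do not have hepatitis B or HIV and baseline safety labs will be monitored prior to receiving study medication".

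The Visit 1 text in Section IV introduces Table 1 as the activities to be completed at screening. For starters, one row of that table holds three items:
- the hepatitis B test, "HBsAg (result from prior test within 12 months acceptable";
- the drug, "Dispense F/TDF or F/TAF for daily dosing to begin 7 days prior to study procedure (PrEP Cohort B only, not already on PrEP";
- the start of virtual directly observed dosing.

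HIV blood, the blood count, liver enzymes and creatinine are in another row, headed "Safety Labs and STI Screening (for participants not undergoing a concurrent endoscopy procedure only". Appendix I likewise says that safety labs, apart from the rectal swab, are not taken in participants having a screening colonoscopy.

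The inclusion criteria require of Cohort B a "documented negative HIV-1/HIV-2 Ag/Ab test in the past 3 months" and a documented negative HBsAg with no time limit. The Cohort A list repeats the latter as "Documented negative HBsAg in those taking study TFV (i.e. cohort B".

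Under the Visit 2 heading, the plan first allows Visits 1 and 2 to be combined where applicable, then states: "After eligibility is confirmed, participants will be contacted to schedule the study visit (Visit 2".

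**The concern.** The protocol names confirmation of hepatitis B and HIV status, with baseline labs, as the mitigation for giving study tenofovir. The table that staff will follow does not secure that order. A starter whose status rests on blood drawn at Visit 1 could be handed the tablets before the result exists, and the text describes no hold, release or retrieval step. A starter who comes in through a clinical endoscopy could receive drug with no study safety labs at all.

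There is also a smaller analytic stake. Objectives 1(b) and 2(b) compare HIV-negative with HIV-positive persons. Each age-by-cohort cell has 10 participants, so one undetected HIV infection counted in Cohort B would be 1/10 = 10% of its cell. This could arise mainly where HIV status rests only on a prior test.

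**Working it through.** The plan gives no figure to reproduce. The check sets the passages side by side and adds day counts.

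**Inputs**
- Cohort B: 10 younger + 10 older = 20 (Section III). The share who are starters is not given, so the number affected is 0 to 20.
- Longest interval from Visit 1 to Visit 2: 42 days (Section IV, Overview).
- Lead-in: dosing begins 7 days before the procedure (Table 1, Appendix I).
- Accepted prior HBsAg: 12 months, taken as 365 days (Table 1).
- Accepted prior HIV test: 3 months, taken as 365/4 ≈ 91 days (Cohort B item 2).
- Date from which these windows are counted: not stated. Both screening and first dose are tried, as assumptions.

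**1. Receipt of drug.** Section VIII puts confirmation before receipt. Table 1 puts the tests and the dispensing at one visit. The two agree for a starter who arrives with acceptable prior results. They disagree for a starter whose HBsAg or HIV status depends on that day's blood, unless results return during the visit, which the text does not provide for.

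**2. First dose.** The first dose is timed from the Visit 2 procedure, and Visit 2 is scheduled after eligibility is confirmed. That is a gate before dosing. It weakens when Visit 2 is tied to a clinical endoscopy already booked, because the date that fixes the first dose then exists before eligibility is settled. The Table 2 eligibility check falls after all seven doses.

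**3. Gap from Visit 1 to first dose.** Gap = (Visit 1 to Visit 2 interval) − 7.
- Longest: 42 − 7 = 35 days.
- Shortest that still fits the lead-in: 7 − 7 = 0 days.

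No minimum gap and no laboratory turnaround time are given, so the day counts do not guarantee that results precede the first dose.

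**4. Greatest age of an accepted prior result at first dose**

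| Test | Window counted to first dose | Window counted to screening |
|---|---|---|
| HBsAg | 365 days | 365 + 35 = 400 days |
| HIV, no blood drawn at Visit 1 | 91 days | 91 + 35 = 126 days |

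Where HIV blood is drawn at Visit 1, that result is at most 35 days old at first dose, so the HIV row of the table does not apply.

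**5. Labs for starters with an endoscopy.** Section VIII promises baseline safety labs before study drug. Table 1 and Appendix I drop them, including creatinine and HIV blood, with a concurrent endoscopy or screening colonoscopy. Neither exempts starters. Appendix I also files HBsAg under safety labs, so its colonoscopy note read literally would drop that test too, whereas Table 1 keeps it in the starters' row.

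**6. Combined visits.** Combining the visits makes the interval 0 days, and dosing dispensed at Visit 1 needs at least 7. The permission names no exception for starters.

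**The case against.** The strongest reply is that Table 1 is an activity list and not a sequence. Its starters' row includes a week of observed dosing, which cannot literally happen at one sitting. Screening before a clinical endoscopy may be by phone, and eligibility assessment is listed ahead of dispensing. Documented negatives are inclusion criteria, screening stops once a participant is found ineligible, and Visit 2 is scheduled only after eligibility is confirmed. The hazards come from taking tenofovir, not from holding unopened tablets.

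Most of this stands. A reader might infer that the plan intends to dose before results are known; the eligibility gate does not support that. But the gate governs enrolment and scheduling, not tablets already handed over, and the safeguard is worded in terms of receipt.

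A reader might also infer that accepting results 3 or 12 months old contradicts the safeguard. It does not: Section VIII sets no recency limit, and a documented prior negative is a form of confirmation. Nor does the 42-day validity note help that reading, since it marks only the blood count and the chemistry panel.

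On combined visits, the qualifier about applicability may be meant to exclude starters, but it does not say so. Finally, Appendix II (HIV Testing Algorithm) was not in the text available for this review, so a hold rule for HIV results there cannot be excluded. The available text shows none for HBsAg. The dispensing row in Appendix I carries no visit mark, which may be an extraction artefact; nothing here relies on it.

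**Conclusion.** The point holds as a conflict over receipt of study drug and an unstated order of results, dispensing and first dose. Two further inconsistencies affect the same participants: safety labs omitted with endoscopy, and combined visits that cannot contain the lead-in. It should be corrected, because the protocol's own mitigation depends on it.

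The reach is at most 20 participants, and fewer if some Cohort B members already take PrEP. The receipt conflict is confined to starters without an acceptable prior result. The windows are an ambiguity and not a contradiction: depending on the assumed anchor, the oldest acceptable HBsAg result at first dose is about 365 or 400 days, and the oldest HIV result about 91 or 126 days. A reader might apply the 126 days to all starters, but it is limited to those with no HIV blood at Visit 1 and also assumes counting from screening. No power or error-rate figure in the plan is affected.

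**What to change.** Reconcile Table 1, the Visit 2 notes, Appendix I, the Cohort B inclusion criteria and the TFV risk paragraph in Section VIII, so that they say the same thing on four matters:
- the order of test results, dispensing and first dose for starters;
- which safety labs apply to starters who have a concurrent endoscopy or screening colonoscopy;
- the date from which the HBsAg and HIV windows are counted;
- whether the option to combine visits applies to starters.

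The result should be consistent with the safeguard in Section VIII, or that statement should be revised to match the procedures. The sponsor and IRB choose the rule; none is proposed here.

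The direct cost is a wording amendment and its IRB review. Sample size and analysis do not change. Any operational cost depends on the rule chosen and falls on at most 20 participants.

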Previous studies have found that age has an effect on CKM expression, post-translational modifications, and activity in multiple tissues.¹¹⁻¹⁶ Thus, it is hypothesized that expression levels and post translational modifications of AK2 and CKM may differ depending upon age, therefore, altering the amount of active TFV-DP and increasing variability of protection. Therefore, it is imperative to investigate expression and post translational modifications of AK2 and CKM in colorectal tissue and PBMCs from various age populations to see if these cellular enzymes change with increasing age.

III. RATIONALE

While PrEP has been shown to be highly effective in reducing the risk of HIV infection, despite adherence to PrEP, some individuals become infected with HIV. To gain an understanding of CKM phosphorylation activity and examine whether CKM might also contribute to variability of TFV-DP activation in colonic CD4+ cells in the presence of HIV infection, we will also measure levels of CKM and TFV-DP in colonic CD4+ T cells of younger and older individuals infected with HIV taking tenofovir-based HIV treatment, as well as those taking tenofovir-based PrEP who are not infected with HIV.

This study is designed to investigate the intracellular AK2 and CKM enzymes in both colorectal tissue and PBMCs in a younger and older adult population. It is hypothesized that age alters expression and post translational modifications and expression of AK2 and CKM in colorectal tissue and PBMCs causing variability in TFV-DP levels in individuals taking tenofovir-based medications.

To test this hypothesis, colorectal biopsies and PBMCs will be collected to assess for changes in AK2 and CKM levels using mass spectrometry and changes in enzymatic activity to phosphorylate TFV from the following populations:

Cohort A: 10 younger (age 18-50) and 10 older (age 65-80) adults who are not infected with HIV and not taking tenofovir-based PrEP ("Control Cohort").

Cohort B: 10 younger (age 18-50) and 10 older (age 65-80) adults who are not infected with HIV, but are taking a TFV-based regimen (either on daily TFV- based PrEP or agree to take a daily TFV-based regimen 7 days prior to procedure). ("PrEP Cohort")

Cohort C: 10 younger (age 18-50) and 10 older (age 65-80) adults who are infected with HIV, taking a TFV-based regimen. ("ARV Cohort")

Study Objectives:

Objective	Endpoint

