1. Determine if levels and activity of AK2 and CKM in colorectal tissue differ between (a) younger adults (age range 18-50 years), and older adults (age range 65-80) or	
 • Proteomics will be used to measure intracellular protein levels and modification status of kinases that phosphorylate TFV. • In individuals taking a TFV-containing regimen, colorectal tissue TFV-DP will be measured at steady-state.

(b) between HIV negative and HIV positive persons.
	
 In individuals not taking a TFV-based regimen, in vitro incubation of TFV with colorectal tissue biopsies will be performed to measure TFV activation as a function of age.

2. Determine if levels and activity of AK2 and CKM in PBMCs differ between:
 
(a) younger adults, defined as 18-50 years of age, and older adults, defined as 65-80 years of age or
 
(b) HIV negative and HIV positive persons..
	
 Proteomics will be used to measure intracellular protein levels and modification status of kinases that phosphorylate TFV. In individuals not taking a TFV-based regimen, in vitro incubations of TFV with PBMCs will be performed to measure TFV activation as a function of age. In individuals taking a TFV-containing regimen, colorectal tissue TFV-DP will be measured at steady-state.

IV. STUDY DESIGN

Overview

The design of the study will be a two-visit study, including a screening visit (Visit 1) and a sampling visit (Visit 2). During the screening visit, the individual will be assessed for eligibility. For participants scheduled for sigmoidoscopy or colonoscopy for a medical indication, the screening visit may be conducted by phone prior to the procedure. If eligible, the participant will return for the study visit ≤ 42 days following the screening visit. During the study visit, approximately 100 mL of blood will be drawn for PBMC isolation. Following the blood draw, participants will undergo endoscopic evaluation in which 10 colorectal biopsy samples will be obtained between 10-20 cm from the anal verge. Thirty adults from each age population (younger and older) will be enrolled for this study. Three cohorts (each including young and old groups) will be defined by TFV administration and HIV status.

Study Population

Three cohorts of participants will be recruited, with 10 younger and 10 older in each cohort.

Cohort A: Healthy Volunteers, not taking TFV based PrEP (Control Cohort)

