Incidental Findings: Significant clinical findings may be discovered during study procedures, which may warrant referral for medical care and further testing. If significant clinical findings are discovered during the procedure, study subjects will be referred to the proper Johns Hopkins Division for additional evaluation and treatment as necessary.

Social Risk: Although the study site will make every effort to protect participant's privacy and confidentiality, it is possible that involvement in the study could become known to others, and that social harms may result (i.e., subjects could become known as HIV-infected or at "high risk" for HIV infection) and, consequently, be treated unfairly or discriminated against by families, friends and/or communities.

Loss of confidentiality: Although every effort will be made to protect the privacy and confidentiality of all participants, it is possible that their involvement in the study could become known to others. All guidelines for the protection of Personal Health Identifiers will be followed.

Benefits

There are no direct benefits to subjects who participate in this study. However, there may be personal satisfaction in the knowledge that they are aiding in important medical research, and that the knowledge obtained from this study will advance the field of HIV prevention. Participants will be reimbursed for their time and inconvenience.

The risks to individual participants are outweighed by potential benefits to the scientific community and to society – namely, contribution to our microbicide knowledge-bank.

IX. STATISTICAL ANALYSIS

To compare protein levels between the younger adult and older adult groups, protein abundances will be averaged within age groups. Differences in protein levels will be determined by unpaired two-tailed t test using the Benjamini-Hochberg correction for multiple comparisons, with significant differences being defined as having an adjusted p-value of <0.05. Based on our previous studies of TFV phosphorylation we estimate ~80% power to detect a 1.5-fold difference between study groups using our measured outcomes and >95% power to detect a 1.75-fold difference between study groups at our sample size.

X. CONFIDENTIALITY

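### The age comparison in Section IX ignores the three-cohort design and does not say whether it is pooled; a log-scale model with age and cohort costs almost nothing, may gain power, and supplies the missing HIV-status test.

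*Combined protocol and SAP*

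**What the plan says.** Section IX (Statistical Analysis) describes one comparison, younger against older. As a first step, "protein abundances will be averaged within age groups". The test itself is given in these terms: "Differences in protein levels will be determined by unpaired two-tailed t test using the Benjamini-Hochberg correction for multiple comparisons". The threshold is 0.05 after adjustment. The section claims about "80% power to detect a 1.5-fold difference between study groups" and more than 95% at 1.75-fold. It gives no SD, analysis scale, cohort factor or number of tests, and does not say which groups the power figure refers to.

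Section IV (Study Population) sets the design: "Three cohorts of participants will be recruited, with 10 younger and 10 older in each cohort". The Overview adds: "Three cohorts (each including young and old groups) will be defined by TFV administration and HIV status". From the Rationale, A is HIV-negative without TFV, B is HIV-negative on TFV, and C is HIV-positive on TFV.

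In the Study Objectives table, parts 1(b) and 2(b) ask whether the kinases differ by HIV status in tissue and in PBMCs. Proteomics is listed without restriction to a cohort. TFV-DP is measured only in those on TFV (B and C), and in vitro activation only in those not on TFV (A).

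**The concern.** The plan enrols by cohort and asks whether one cohort factor, HIV status, changes the kinases. The age test then treats cohort as if it did not exist. If cohorts differ, that difference sits in the error term of a pooled age test and weakens the lead comparison. If the test is meant per cohort, two thirds of the data are left out of each test. The text does not say which.

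Objectives 1(b) and 2(b) also have no stated test and no place in the Benjamini-Hochberg family. The HIV contrast could therefore be chosen after the data are seen, and the possible choices do not answer the same question.

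**Working it through.** **Inputs from the documents.** 3 cohorts × 2 age groups × 10 = 60 participants; two-sided 5%; 1.5-fold (ln 1.5 = 0.4055) at about 80% power; 1.75-fold at more than 95%.

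**Inputs assumed.** The log-SD within cohort and age group (σ), the cohort differences, and the number of tests.

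**The plan's own figure.** Without an SD or a group size, the 80% cannot be reproduced forward. Solving the noncentral t for the natural-log SD that gives 80% at 1.5-fold yields 0.306 (10 v 10), 0.446 (20 v 20) or 0.551 (30 v 30). Each gives 97% at 1.75-fold, so the two stated powers agree with each other but do not reveal the group size.

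**No bias.** With 10 per cell, cohort effects cancel from the age difference. Its true standard error is σ√(2/30) with or without a cohort term; at σ = 0.551 that is 0.1423.

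**What pooling does to the error term.** The expected error variance of the pooled t test is σ² + 20·Σ(c − c̄)²/58, where c are the three cohort effects on the log scale. For an equal step s from A to B to C, the added term is 40(ln s)²/58. At σ = 0.551 (σ² = 0.3036), the noncentrality is 0.4055/0.1423 = 2.850 and the critical t is 2.0017 on 58 df.
- Step 1.25: added 40 × 0.0498/58 = 0.0343. SD ratio √(0.3379/0.3036) = 1.055. Effective critical value 2.0017 × 1.055 = 2.112. Power ≈ Φ(2.850 − 2.112) = 77.0%.
- Step 1.5: added 40 × 0.1644/58 = 0.1134. SD ratio √(0.4170/0.3036) = 1.172. Effective critical value 2.346. Power ≈ Φ(0.504) = 69.3%.

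**Cost of the cohort term.** The critical t rises from 2.0017 (58 df) to 2.0032 (56 df). With equal cohorts, power goes from 80.00% to 79.95%.

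**Simulation** (40,000 replicates, lognormal data, 1.5-fold age effect, unadjusted 5%; power in %, pooled log t test → model with cohort):

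| Assumed cohort pattern | σ 0.551 | σ 0.446 | σ 0.306 |
|---|---|---|---|
| Equal | 79.8 → 79.7 | 93.4 → 93.4 | 99.9 → 99.9 |
| Step 1.1 | 79.4 → 80.0 | 93.0 → 93.4 | 99.9 → 99.9 |
| Step 1.25 | 76.6 → 79.7 | 91.0 → 93.4 | 99.7 → 99.9 |
| Step 1.5 | 68.8 → 79.7 | 84.0 → 93.4 | 98.2 → 99.9 |
| Only C differs, 1.25-fold | 79.3 → 80.3 | – | – |
| Only C differs, 1.5-fold | 77.0 → 80.3 | – | – |

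These agree with the formula to about half a point. At σ = 0.551 the type I error of the pooled t test is 3.9% (step 1.25) and 2.2% (step 1.5); the model stays at 5%.

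**After Benjamini-Hochberg** (assumed family of four independent age tests: AK2 and CKM in tissue and PBMCs; one truly different). At σ = 0.551: 61.7 → 61.4 (equal), 55.6 → 61.1 (step 1.25), 45.2 → 62.3 (step 1.5). At σ = 0.306: 98.0 → 99.3 (step 1.25), 89.3 → 99.3 (step 1.5).

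**If the test is per cohort.** At 10 v 10, unadjusted power is 34% (σ = 0.551) or 80% (σ = 0.306). Using all 60 participants it is 80% or 99.9%.

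**HIV status.** For C v B at 1.5-fold, with a 1.5-fold age effect present, plain log t → model: 57 → 63% (σ = 0.551), 74 → 81% (0.446), 95 → 98% (0.306). Now suppose only TFV use matters, with A 1.5-fold away from B and C. C v A+B is then shifted by 0.4055/2 = 0.2027 with standard error 0.551√(1/20 + 1/40) = 0.1509, and rejects 26% of the time with no HIV effect (38% at σ = 0.446, 66% at 0.306). C v B rejects 5%.

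**Families.** With one true age effect, the first Benjamini-Hochberg threshold is 0.05/4 = 0.0125 in a four-test age family and 0.05/8 = 0.00625 if four C v B tests join it. At σ = 0.551 and 56 df, power at those levels is 61% and 51%.

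**The case against.** The planned test is valid, and everything beyond that is conditional. Much of this stands.

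- **Calibration.** The table adds cohort variance on top of σ = 0.551. If 0.551 is instead the total SD across cohorts, the figures are 80.2 → 80.7% (step 1.1), 81.1 → 84.1% (step 1.25) and 84.7 → 93.9% (step 1.5), and the planned test never falls below the stated 80%. A reader might infer that the study is underpowered; with no SD given, the documents do not support that. The gain from the model is similar at modest steps under either reading.
- **Size of cohort differences.** A 1.5-fold step puts C at 1.5 × 1.5 = 2.25-fold from A, more than the 1.75-fold difference in the power statement, and no section documents such a gradient. In the mild cases the gain is about 1 point or less.
- **Bias.** A reader might infer that ignoring cohort confounds the age comparison or inflates false positives. Equal cells rule out the first, and the simulated type I error is below 5%, not above it. Confounding by cohort could arise only if enrolment ends unbalanced.
- **Scale.** The test may already be planned on logs, so a raw-scale analysis cannot be charged to the plan.
- **C v B is not clean.** Cohort B mixes ongoing PrEP with 7-day dosing, and TDF and TAF are both allowed, so B and C may differ in prodrug and duration of use.
- **Common age effect.** The additive model assumes one. Power for a 1.5-fold age-by-cohort interaction between two cohorts is only about 21% (σ = 0.551) to 54% (0.306).

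None of this argues for leaving cohort out, because the downside is about 0.05 point of power. The absence of a stated HIV-status test needs no assumption at all.

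**Conclusion.** The point holds as an efficiency and specification point. Section IX should say whether the age test is pooled, should use the cohorts the design already has, and should name the HIV contrast. The size of the power gain rests on assumed SDs and cohort differences. At residual log-SD 0.551, unadjusted, it runs from nil (equal cohorts) through about 1 point (only C differs, 1.25-fold) and 3 points (step 1.25) to about 11 (step 1.5). At log-SD 0.306 it is under 2 points unadjusted in every pattern tried; after Benjamini-Hochberg in the assumed family of four it reaches 10 points, but only at the 1.5-fold step. Worth changing before analysis, but no result obtained under the present plan would be invalid for this reason.

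**What to change.** In Section IX:

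1. **Proteomic abundances.** Replace the t test by a linear model on log2 abundance with age group and three-level cohort as factors, fitted to all 60 participants, one model per protein and compartment. Report the age effect as a ratio of geometric means with 95% CI.
2. **Tissue TFV-DP.** Use the same model with a two-level cohort factor (B, C).
3. **In vitro activation (Cohort A only).** Use a two-group comparison on logs.
4. **HIV status, objectives 1(b) and 2(b).** Take C v B from the proteomic model. It is the only HIV contrast with both cohorts on TFV; note that prodrug and duration may still differ. Report C v A+B descriptively, outside the testing family, because it mixes HIV status with TFV use.
5. **Multiplicity.** Use one Benjamini-Hochberg family for the age p-values and one for the C v B p-values, and list the proteins, compartments and modification measures in each. FDR is then controlled within each family, not across both.

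The cost is SAP wording and a small change to the analysis code, with no new data. The model uses 2 df for proteomics (about 0.05 point of power) and 1 df for TFV-DP (at most 0.06 point).
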